4.2.2. Study Day

If a visit/reporting date is on or after Day 1, then the study day at the visit/reporting date will be calculated as

$$\text{Day \#} = (\text{Visit/Reporting Date} - \text{Day 1 date} + 1).$$

If the visit/reporting date is before Day 1, then the study day at the visit/reporting date will be calculated as

$$\text{Day \#} = (\text{Visit/Reporting Date} - \text{Day 1 date}).$$

A study day of -1 indicates 1 day before Day 1.

4.2.3. Baseline Value

Baseline is the last nonmissing measurement obtained before the first administration of any study drug (epacadostat, pembrolizumab, or azacitidine) is administered to subjects.

When scheduled assessments and unscheduled assessments occur on the same day and time of the assessment or time of first dose is not available, use the following convention to determine baseline:

- If both a scheduled and an unscheduled visit are available on the day of the first dose and the time is missing, use the scheduled assessment as baseline.
- If all scheduled assessments are missing on the day of the first dose and an unscheduled assessment is available, use the unscheduled assessment as baseline.

4.2.4. Handling of Missing and Incomplete Data

In general, values for missing data will not be imputed unless methods for handling missing data are specified in this section or relevant sections.

Partial disease/cancer diagnosis date will be handled as follows:

- If only the day is missing, then the imputed day will be the first of the month.
- If both the month and day are missing, then the imputed day and month will be 01 JAN.
- No imputation will be done if the date is completely missing.

Missing or partial date of last dose will be handled as follows:

- If only the day is missing, then the imputed date of the last dose will be the earlier date of the first day of the month or the date that the subject discontinued treatment.
- Otherwise, the date that the subject discontinued treatment will be used as the date of the last dose.

For relevant efficacy endpoints, partial death date will be imputed as follows:

- If mmyyyy for the last contact date = mmyyyy for the death date, then the death date will be set to the day after the last contact date.
- If mmyyyy for the last contact date < mmyyyy for the death date, then the death date will be set to the first day of the death month.
- Otherwise, the partial death date will not be imputed.

For prior and concomitant medications:

The start/stop dates recorded in the eCRF by the investigator and his or her research staff will be used to identify when a concomitant medication was taken during the study. Any missing start date must be queried for resolution. Unresolved missing start dates will be handled as follows:

- If the date is completely missing, the medication will be considered both prior and concomitant.
- If only the day is missing, and the last day of the month is before the first dose date on Day 1, then the concomitant medication will be considered as starting before Day 1, and the incomplete date will be imputed as the last day of the month.
- If only the day is missing, and the first day of the month is after the first dose date on Day 1, then the concomitant medication will be considered as starting after Day 1, and the incomplete date will be imputed as the first day of the month.
- If only the day is missing, and the month is equal to the month of the first dose date on Day 1, then the incomplete date will be imputed as the first day of the month.
- If both the month and day are missing, and the last day of the year is before the first dose date on Day 1, then the concomitant medication will be considered as starting before Day 1, and the incomplete date will be imputed as if it is the last day of the year. Otherwise, the incomplete date will be imputed as if it is the first day of the year.

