6.4.1. Exposure for Epacadostat

Exposure for epacadostat will be summarized as follows:

- **Duration of treatment (days):** Date of last dose of epacadostat – date of first dose of epacadostat + 1.
- **Average daily dose (mg/day):** Total dose administered (mg) / duration of treatment (days).
- Number and percentage of subjects with 0 to 3, > 3, > 6, and > 9 months duration of exposure.

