6.4.2. Exposure for Pembrolizumab

Exposure for pembrolizumab will be summarized as follows:

- **Total number of infusions:** Total number of infusions per subject with a nonzero dose of pembrolizumab.
- **Total dose administered (mg):** Sum of the cumulative dose of pembrolizumab that has been administered.

For an infusion i , let C_i be the concentration (mg/mL) of pembrolizumab and V_i be the total volume administered (in mL) reported on the pembrolizumab dosing eCRF; let N be the total number of infusions

$$\text{Total dose administered (mg)} = \sum_{i=1}^N C_i \times V_i$$

- **Duration of treatment (days):** Date of last dose of pembrolizumab – date of first dose of pembrolizumab + 1.

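### A last-dose date with the day missing is set to the first of the month with no lower bound, so treatment duration can be zero, negative or too short

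*SAP*

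**What the plan says.** SAP 4.2.4 opens by confining imputation to written rules: "values for missing data will not be imputed unless methods for handling missing data are specified in this section or relevant sections". For a missing or partial last-dose date it gives two.

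- Only the day is missing: "the imputed date of the last dose will be the earlier date of the first day of the month". If treatment was stopped before then, the discontinuation date is used instead.
- Any other missing or partial date: "Otherwise, the date that the subject discontinued treatment will be used as the date of the last dose".

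The resulting date enters the exposure definitions. SAP 6.4.1 defines epacadostat duration as "Date of last dose of epacadostat – date of first dose of epacadostat + 1", and SAP 6.4.2 defines pembrolizumab duration as "Date of last dose of pembrolizumab – date of first dose of pembrolizumab + 1". SAP 6.4.3 uses the same form for azacitidine. For epacadostat, duration is also the denominator of average daily dose and the basis of the exposure categories: "Number and percentage of subjects with 0 to 3, > 3, > 6, and > 9 months duration of exposure". None of SAP 6.4.1 to 6.4.3 adds a check on the imputed date.

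**The concern.** When only the day is unknown, the rule picks the earliest possible day. Adding the discontinuation date does not help, because taking the earlier of two dates can only keep the first of the month or move further back. Nothing stops the imputed date from falling before the first dose, or before a dose already on record.

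The rule also sits oddly beside its neighbours in SAP 4.2.4. A last-dose date with less information (month also missing) goes to the discontinuation date, while one with a known month goes to the earliest day. The partial death-date rule does have a floor: when the month matches that of last contact, death is placed on the day after last contact. Medication start dates are compared with the first dose. SAP 4.2.4 calls for queries of missing medication start dates, and SAP 8.2.1 does so for adverse-event onset dates. Neither section asks for a query of a partial last-dose date.

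At stake are the exposure summaries, reported by dose level. SAP 3.4.1.1 plans 3 to 9 subjects per escalation level, so one impossible value could visibly distort a mean or minimum.

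**Working it through.** The plan states no figure on this point, so there is none to reproduce. The check applies its formulas to assumed dates.

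**Inputs**
- Imputed last dose = the earlier of the first of the recorded month and the discontinuation date (SAP 4.2.4).
- Duration = last − first + 1 (SAP 6.4.1 to 6.4.3).
- Average daily dose = total dose ÷ duration (SAP 6.4.1, epacadostat only).
- Illustrative epacadostat dose: 100 mg twice daily = 200 mg/day (SAP 3.1.2.1, Cohort 1).
- Assumed: calendar dates are illustrative; discontinuation is not before the first of the recorded month; total dose runs to the true last dose.

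**1. First and last dose in the same month.** With the first dose on day *d*, duration = 1 − *d* + 1 = 2 − *d*.
- *d* = 12: −10 days.
- *d* = 2: 0 days, and average daily dose is undefined.
- First dose 10 March, true last dose 28 March: true duration 19 days, total dose 19 × 200 = 3,800 mg. Imputed duration is 2 − 10 = −8 days, and the average is 3,800 ÷ (−8) = −475 mg/day.

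A negative duration fits none of the exposure categories, which start at 0.

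**2. All other cases.** The shortfall is the true day of the month minus 1, so 0 to 30 days. If the true day is uniform over a 30-day month, the mean is (0 + 1 + … + 29) ÷ 30 = 14.5 days.

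**3. Effect on epacadostat average daily dose.** At the mean shortfall, the overstatement for a true duration *D* is *D* ÷ (*D* − 14.5).

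| True duration (days) | Calculation | Ratio |
|---|---|---|
| 42 | 42 ÷ 27.5 | 1.53 |
| 63 | 63 ÷ 48.5 | 1.30 |
| 180 | 180 ÷ 165.5 | 1.09 |
| 270 | 270 ÷ 255.5 | 1.06 |

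**4. A single example near the upper end.** First dose 24 March, true last dose 25 May: 8 + 30 + 25 = 63 days. Imputed to 1 May: 8 + 30 + 1 = 39 days. The ratio is 63 ÷ 39 = 1.62, so 200 mg/day reads as about 323 mg/day.

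**5. A later dose on record is ignored.** First dose 10 March, true last dose 28 April: 50 days, 10,000 mg. The rule gives 1 April and 23 days even if a dose on 21 April is documented. The average reads 10,000 ÷ 23 = 435 mg/day.

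**6. The other two drugs.** Azacitidine average dose is per administration (SAP 6.4.3), and no average is defined for pembrolizumab (SAP 6.4.2). Only their durations depend on the imputed date.

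**The case against.** The best defence is that the rule will rarely be used. Site staff give pembrolizumab and azacitidine and document each administration (Protocol 5.3). For epacadostat, diaries record the last dose before each visit (Protocol 7.10.1), the last-dose date goes into the case report form (Protocol 5.5.2), and entries must be verifiable against source (Protocol 10.3). Negative durations would also show up in listings. This stands as an argument about frequency. It does not repair the rule, and epacadostat, which is largely taken at home, is both the likeliest drug to have a partial date and the only one with an average daily dose.

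A reader might infer more than the documents support:

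- **That the rule always shortens exposure.** If the true last dose was on the 1st, the imputed date is exact.
- **That average daily dose is inflated in every affected subject, typically by 62%.** With zero or negative duration it is undefined or negative, not inflated. The 62% comes from a short course ending late in a month. Any inflation also assumes that total dose does not depend on the imputed date. SAP 6.4.1 does not say how that total is derived; SAP 6.5 uses drug accountability, but for compliance. If the total were built only up to the imputed date, numerator and denominator would shrink together and the inflation would largely vanish.
- **That efficacy or adverse-event results are affected.** Treatment emergence in SAP 8.2.1 is defined from the first dose, with no end window tied to the last dose. The response, duration of response and progression-free survival rules in SAP 7.2 do not use the last-dose date.

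**Conclusion.** The point holds as a defect in a stated rule. Followed literally, SAP 4.2.4 gives zero or negative treatment duration whenever first and last dose share a month and the first dose is after the 1st. In other cases it shortens duration by 0 to 30 days. The mean of 14.5 days assumes a uniform true day in a 30-day month. The 1.30 and 1.09 ratios also assume a total epacadostat dose counted independently of the imputed date.

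The consequence is minor. Only descriptive exposure summaries change, and the documents do not say how many last-dose dates will be partial. The number is probably small.

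**What to change.** Replace the day-missing rule in SAP 4.2.4 with one bounded on both sides: impute the earlier of the last day of the recorded month and the treatment discontinuation date, and never earlier than the first dose or the latest documented administration of that drug.

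Two simpler repairs fall short. A floor at the first dose alone turns the 10 to 28 March example into 1 day and 3,800 mg/day. Using a drug-accountability date as a floor is unsafe, because it records a tablet count rather than a dose and can push the date past the recorded month.

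Under the bounded rule, 10 to 28 March with discontinuation on 29 March gives 20 days and 3,800 ÷ 20 = 190 mg/day (true: 19 days, 200 mg/day). For 10 March to 28 April with discontinuation on 29 April, it gives 51 days and 10,000 ÷ 51 = 196 mg/day (true: 50 days, 200 mg/day).

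The cost is one sentence in the SAP and a small programming change. The downside is that exposure may be somewhat overstated when a subject stopped well before both month end and the recorded discontinuation date. In the 24 March to 25 May example with discontinuation after May, duration would be 8 + 30 + 31 = 69 days instead of 63, and the average 12,600 ÷ 69 = 183 mg/day. It would also help to state in SAP 6.4.1 how total epacadostat dose is derived.

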4.2.5. Cycle Length and Duration

For Treatment Group A, Cycle 1 Day 1 is the day that the first dose of pembrolizumab is administered. Scheduled cycle length is 21 days. Actual Day 1 of subsequent cycles will correspond with the first day of administration of pembrolizumab for Treatment Group A in that cycle; thus, treatment cycles may become out of sync with the originally planned schedule, and cycle length may be different from 21 days (\pm 3-day window for subsequent cycles). The date of Day 1 of subsequent cycles recorded on the eCRF will be used as Day 1 of the subsequent cycles.

4.3. Variable Definitions

The following variables will only be calculated if not reported on the eCRF.

4.3.1. Age

Subject age will be calculated as the integer part of the number of years from date of birth to the date of signing the informed consent form, using the following formula:

$$\text{Age} = \text{integer part of } (\text{date of informed consent} - \text{date of birth} + 1) / 365.25.$$

When date of birth was not collected for a subject, and the age of the subject was reported in the eCRF, the reported age will substitute for the calculated age.

4.3.2. Body Mass Index

Body mass index will be calculated as follows:

$$\text{BMI (kg/m}^2\text{)} = [\text{weight (kg)}] / [\text{height (m)}]^2.$$

4.3.3. Prior and Concomitant Medication

Prior medication is defined as any nonstudy medication started before the first dose of epacadostat, pembrolizumab, or azacitidine.

Concomitant medication is defined as any nonstudy medication that is started accordingly:

- Before the date of first administration of epacadostat, pembrolizumab, or azacitidine, and is ongoing throughout the study or ends on/after the date of first study drug administration.
- On/after the date of first administration of epacadostat, pembrolizumab, or azacitidine and is ongoing or ends during the course of study drug.

A prior medication could also be classified as "both prior and concomitant medication" if the end date is on or after first dose of epacadostat, pembrolizumab, or azacitidine. In the listing, it will be indicated whether a medication is prior-only, concomitant-only, or both prior and concomitant medication.

For the purposes of analysis, all medications will be considered concomitant medications unless the medications can unequivocally be defined as not concomitant.

5. STATISTICAL METHODOLOGY

5.1. General Methodology

Unless otherwise noted, SAS[®] software (SAS Institute Inc, Cary, NC; v9.4 or later) will be used for the generation of all tables, figures, and statistical analyses. Descriptive summaries for continuous variables will include, but not be limited to, the number of observations, mean, standard deviation, median, minimum, and maximum. Descriptive summaries for categorical variables will include the number and percentage of subjects in each category. Summary tables and figures will be provided only for initial treatment phase. Only listings will be provided for re-treatment phase, if applicable.

5.2. Treatment Groups

This is an open-label, multicenter, Phase 1/2 study evaluating the addition of an epigenetic priming regimen to an immunotherapy doublet in subjects with advanced or metastatic solid tumors. The study will be conducted in 2 parts.

Due to the stop of study enrollment, only subjects in Treatment Group A have been enrolled into Parts 1 and 2. Data from Parts 1 and 2 for Treatment Group A will be summarized together by dose level. The dose levels for Treatment Group A are shown in [Table 1](#).

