In addition to the 6 Simon 2-stage safety/efficacy expansion cohorts, another 9 treatment sequencing tumor biopsy cohorts will be emolled to evaluate epigenetic and tumor microenvironment changes. A total of 25 subjects will be emolled in each Expansion Cohorts A-3, A-4, B-9 through B-11 and C-11 through C-13, and 10 first-line melanoma subjects will be emolled in Expansion Cohort A-5.

In the Part 2 treatment sequencing tumor biopsy cohorts, assuming the true rate of subjects positive for the biomarker is 70%, the probability of observing 16 or more subjects out of 25 subjects with the biomarker is 81% for Expansion Cohorts A-3, A-4, B-9 through B-11, and C-11 through C-13 and the probability of observing 6 or more subjects out of 10 subjects with the biomarker is 85% for Expansion Cohort A-5.

All statistical analyses are descriptive in nature. Descriptive statistics will be deduced where appropriate. Continuous endpoints will be summarized with number of subjects, mean, standard deviation, minimum, median, and maximum for each cohort. Categorical endpoints will be summarized with frequency and percent for each cohort.

If data warrants, ORR will be estimated with 95% exact confidence interval. Time to event endpoints such as DOR, PFS, and OS will be summarized with Kaplan-Meier estimates by cohort.

TABLE OF CONTENTS

SYNOPSIS	3
LIST OF ABBREVIATIONS.....	31
1. INTRODUCTION	36
1.1. Innunotherapy in Cancer	36
1.2. Overview of Pembrolizumab.....	38
1.3. Overview of Epacadostat.....	38
1.4. Overview of Azacitidine.....	40
1.5. Overview of iNCB057643.....	41
1.6. Overview of iNCB059872.....	44
1.7. Study Rationale.....	46
1.7.1. Rationale for Combining Epigenetic Therapy With Innunotherapy	46
1.7.2. Justification for the Treatment Regimen	48
1.7.3. Rationale for Phase 2 Subject Populations	52
1.7.3.1. Non-Small Cell Lung Cancer.....	52
1.7.3.2. Microsatellite Stable Colorectal Cancer	54
1.7.3.3. Treatment Sequencing Tumor Biopsy Cohort Indications	55
1.8. Potential Risks and Benefits of the Treatment Regimen	55
■ [REDACTED]	55
1.8.2. Risks From Pembrolizumab	57
1.8.3. Risks From Azacitidine	57
1.8.4. Risks From INCB057643	57
1.8.5. Risks From INCB059872	58
1.8.6. Risks From Combination Therapy.....	58
2. STUDY OBJECTIVES AND ENDPOINTS.....	59
2.1. Study Objectives.....	59
2.1.1. Primary Objectives	59
2.1.2. Secondary Objectives	59
■ [REDACTED]	59
2.2. Study Endpoints.....	60
2.2.1. Primary Endpoints	60
2.2.2. Secondary Endpoints	60

		61

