9.4.2. Secondary Analyses

Part 1: The proportion of subjects with advanced or metastatic solid tumors who meet the objective response criteria (CR + PR), as per RECIST v1.1, will be estimated with 95% CI.

Part 2: The clinical safety data (vital signs, ECGs, routine laboratory tests, and AEs) for subjects with previously treated Stage IV or recurrent NSCLC, Stage IV MSS CRC, and other select solid tumors will be summarized using descriptive statistics (eg, mean, frequency) using the safety population, which is detailed in Section 9.4.4.

Parts 1 and 2: The percentage of TIL responders for subjects with advanced or metastatic solid tumors and previously treated Stage IV or recurrent NSCLC and Stage IV MSS CRC will be estimated with 95% CI. A subject is considered a TIL responder if the subject has an increase in the number of TILs or the ratio of CD8+ lymphocytes to Tregs infiltrating tumor post-treatment versus pretreatment with pembrolizumab and epacadostat in combination with azacitidine, INCB057643, or INCB059872 evaluated by IHC.

Parts 1 and 2: PFS and DOR of subjects with advanced or metastatic solid tumors and previously treated Stage IV or recurrent NSCLC and Stage IV MSS CRC will be estimated using Kaplan-Meier method as per RECIST v1.1 if there are enough observations.

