2.2.2. Secondary Objectives

- Part 1: To evaluate the efficacy of the combination in subjects with advanced or metastatic solid tumors by assessing ORR per RECIST v1.1 at the MTD, maximum tested dose, or PAD.
- Part 2: To evaluate the safety and tolerability of the combinations in subjects with previously treated Stage IV or recurrent NSCLC, Stage IV MSS CRC, and select solid tumors at the MTD, maximum tested dose, or PAD.
- Parts 1 and 2: To evaluate changes in T-cell infiltration in the tumor microenvironment with the combinations in subjects with advanced or metastatic solid tumors, previously treated Stage IV or recurrent NSCLC, and Stage IV MSS CRC.
- Parts 1 and 2: To evaluate the efficacy of the combinations in subjects with advanced or metastatic solid tumors, previously treated Stage IV or recurrent NSCLC, and Stage IV MSS CRC by assessing PFS.
- Parts 1 and 2: To evaluate the efficacy of the combinations in subjects with advanced or metastatic solid tumors, previously treated Stage IV or recurrent NSCLC, and Stage IV MSS CRC by assessing DOR.

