3.1.3. Dose-Expansion Phase

3.1.3.1. Treatment Group A

Once the safety profile of all doses tested has been characterized and the RP2D of the combination has been defined, the cohort expansion will be initiated at the RP2D. The doses selected for expansion will not exceed the MTD or maximum tested dose in Part 1.

The purpose of Phase 2 is to gather additional safety, tolerability [REDACTED] and preliminary efficacy information regarding the triplet combination in select tumor types where there is substantial room for improvement over mono- and doublet immunotherapies. The expansion will include:

1. Safety/efficacy cohorts in NSCLC (A-1) and MSS CRC (A-2) (2 tumor biopsies are required)
2. Treatment sequencing biopsy cohorts (3 tumor biopsies are required)
 - a. A-3: azacitidine monotherapy followed by the pembrolizumab/epacadostat doublet
 - b. A-4: pembrolizumab/epacadostat doublet followed by azacitidine
 - c. A-5: pembrolizumab monotherapy followed by epacadostat and azacitidine

Note: Only subjects with untreated (first-line) melanoma will be treated in the pembrolizumab monotherapy cohort (A-5).

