7.2.2. Objective Response Rates and Best Overall Response

A subject is defined as an objective responder if the subject has an overall response of CR or PR at any postbaseline visit prior to first PD. Objective responders will be assessed based on RECIST v1.1.

Objective response rate is defined as the proportion of subjects with objective responses. Objective response rate will be estimated with 95% CIs overall by cohort-specific tumor type. CIs will be calculated based on the method for Simon 2-stage CIs of response rates outlined in Koyama and Chen (2008). Subjects who do not have sufficient baseline data to ascertain response will be included in the denominators in the calculation of ORR.

In general, the best response is determined on subject level using the highest overall response achieved postbaseline prior to and including the first PD, in the order of CR, PR, SD, PD, and NE. Responses of CR, PR, or SD after a response of PD will not be considered in determining best response by RECIST v1.1 criteria. In the case of SD, measurements must meet the SD criteria at least after the date of first dose at a minimum of 56 days (9 weeks – 7-day window). Subjects who fail to meet this criterion will have best overall response of PD if the next available assessment indicated PD, or NE if there is no additional assessment available.

Under RECIST v1.1, the best response is determined by subject using the highest overall response achieved postbaseline prior to and including the first PD, in the order of CR, PR, SD, PD, and NE. Responses of CR, PR, or SD after a response of PD will not be considered in determining best response by RECIST v1.1 criteria. In the case of SD, measurements must meet the SD criteria at least after the date of first dose of study drug at a minimum of 56 days (9 weeks – 7-day window). Subjects who fail to meet this criterion will have best overall

response of PD if the next available assessment indicated PD, or NE if there is no additional assessment available.

For subjects with measurable disease at baseline, the RECIST v1.1 assessment criteria presented in [Table 11](#) can be used to determine the overall disease status at a given time point based on the target lesion, nontarget lesion, and new lesion assessment.

Table 11: RECIST Evaluation Criteria for Overall Response: Measurable Disease at Baseline

Target Lesions	Nontarget Lesions	New Lesions	Overall Response
CR	CR	No	CR
CR	Non-CR/Non-PD	No	PR
CR	NE	No	PR

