7.2.5. Progression-Free Survival

Progression-free survival will be assessed by RECIST v1.1.

[figure not shown]
Censoring for PFS will follow the algorithm outlined in [Table 12](#), which is based on the FDA Guidance for Industry: Clinical Trial Endpoints for the Approval of Cancer Drugs and Biologics ([FDA 2007](#)).

The KM estimate of median PFS will be presented with its 95% CI. The 95% CI will be calculated using Brookmeyer and Crowley's method (1982).

Table 12: Evaluation and Censoring of Progression-Free Survival

Situation	Outcome	Date of Progression or Censoring
No baseline tumor assessments	Censored	Date of Day 1
No valid postbaseline response assessments	Censored	Date of Day 1
Progression documented between scheduled response assessments	Progressed	Date of first overall response of PD
No progression	Censored	Date of last valid radiologic assessment (not NE and not missing)
Study discontinuation for undocumented progression	Censored	Date of last valid radiologic assessment (not NE and not missing)
Study discontinuation for toxicity or other reason	Censored	Date of last valid radiologic assessment (not NE and not missing)
New anticancer treatment started	Censored	Date of last valid radiologic assessment (not NE and not missing) on/before starting a new anticancer treatment.
Death before first progressive response assessment	Progressed	Date of death
Death between adequate response assessments	Progressed	Date of death
Death or progression after more than 1 missed assessment	Censored	Date of last valid radiologic assessment (not NE and not missing) prior to death

Under RECIST v1.1, PFS is defined as the length of time between the baseline visit (Day 1) and the earlier of death or first assessment of PD. Date of death will be determined using the Death Report, Survival Follow-Up, and Subject Status eCRFs.

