1.5 Others				
1.5.1	Summary of General Medical History	Safety	X	
2 Efficacy				
2.1.1	Summary of Best Response, Duration of Response Under RECIST v1.1 for Subjects in the Initial Treatment Phase	Response Evaluable		X
2.2.1	Summary of Progression-Free Survival Under RECIST v1.1 for Subjects in the Initial Treatment Phase	Response Evaluable		X
█	█	█		█
2.3.2	Summary of Largest Percentage Reduction in Sum of Diameters of Target Lesions	Response Evaluable		
Safety				

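### In the visible SAP the only grouping rule for PFS, and possibly for DOR, is dose-level pooling of Parts 1 and 2, which does not address the NSCLC and MSS CRC objectives

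*SAP*

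**What the plan says.** **Grouping rule.** SAP 5.2, for Treatment Group A: "Data from Parts 1 and 2 for Treatment Group A will be summarized together by dose level". The dose levels are those of SAP Table 1.

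**ORR.** SAP 7.2.2 departs from that rule: "Objective response rate will be estimated with 95% CIs overall by cohort-specific tumor type".

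**PFS.** SAP 7.2.5: "The KM estimate of median PFS will be presented with its 95% CI". It names no cohort, tumor type or dose level. Appendix A plans one table, 2.2.1, titled "Summary of Progression-Free Survival Under RECIST v1.1 for Subjects in the Initial Treatment Phase".

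**DOR.** SAP 7.2.3 gives a Kaplan-Meier median with a 95% CI and no grouping. Table 2.1.1 reports it together with best response.

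**Objectives.** SAP 2.2.2 lists PFS in advanced solid tumors, "previously treated Stage IV or recurrent NSCLC, and Stage IV MSS CRC by assessing PFS", with a parallel objective for DOR.

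**Protocol.** Section 9.4.2 says PFS and DOR in these populations and in "Stage IV MSS CRC will be estimated using Kaplan-Meier method as per RECIST v1.1 if there are enough observations". The synopsis (Statistical Methods) says: "Time to event endpoints such as DOR, PFS, and OS will be summarized with Kaplan-Meier estimates by cohort".

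**Where expansion subjects fall.** SAP 3.1.3.1: "the cohort expansion will be initiated at the RP2D".

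**The concern.** Dose level is a natural axis for safety in Part 1. It is a poor one for PFS once expansion cohorts are added. Because expansion starts at a single recommended dose, most Part 2 subjects fall in one dose row, unless a cohort is restarted at a lower dose for toxicity. That row can hold NSCLC after PD-1 failure (A-1), MSS CRC (A-2), four tumor types in the sequencing cohorts (A-3, A-4), first-line melanoma (A-5) and Part 1 subjects with any solid tumor.

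A single Kaplan-Meier median for that mixture depends on who happened to be enrolled. It does not estimate PFS in NSCLC or in MSS CRC, which the plan names as secondary objectives. The SAP already treats tumor type as the relevant split for ORR, so the different treatment of PFS looks like an oversight.

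**Working it through.** **1. Does the 5.2 rule reach PFS?**

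| SAP item | Grouping stated |
|---|---|
| 5.2, all Treatment Group A data | Dose level, Parts 1 and 2 together |
| 6.1, 6.2, ECG abnormalities in 8.5 | Dose level, repeated |
| 6.4 to 6.6, 8.3, 8.4 | No dose-level grouping named |
| 7.2.2 ORR | Cohort-specific tumor type |
| 7.2.3 DOR | None; shares Table 2.1.1 with best response |
| 7.2.5 PFS, Table 2.2.1 | None |

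Exposure, compliance, medications, laboratory tests and vital signs repeat no dose-level grouping and must take theirs from 5.2. Silence in 7.2.5 therefore does not signal some other layout. For DOR the shared table leaves two readings open.

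**2. Who would be in the row?**

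Inputs: 8 subjects each in A-1 and A-2 (Stage 1 size, SAP Table 10); p = 3 to 9 Part 1 subjects at that dose (SAP 3.4.1.1); s = 0 to 60 in A-3 to A-5 (protocol 4.3.1). The SAP (section 9) says the study ended before the Part 2 interim analyses, so Stage 1 sizes are a reasonable working assumption.

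NSCLC cohort share = 8 / (16 + s + p)

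- s = 0, p = 3: 8/19 = 42%
- s = 60, p = 9: 8/85 = 9%

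At the planned maxima (27 in each Simon cohort, 60 in sequencing, p = 3 to 9) the share is 27/117 = 23% to 27/123 = 22%.

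These are illustrations, not bounds. Protocol 4.3.2 allows replacement for unmet biopsy requirements or DLT non-evaluability, and a replaced subject who was dosed can stay in the response evaluable population (SAP 5.3.1). Protocol 9.6 also lets enrollment continue if enough responders are seen early.

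**3. What would the pooled median describe?**

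Assume exponential PFS. With A-1 and A-2 only, 8 each, medians 2 and 4 months, the pooled median t solves

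½·0.5^(t/2) + ½·0.5^(t/4) = 0.5.

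Put x = 0.5^(t/4). Then x² + x = 1, x = 0.618, and t = 4 × log₂(1/0.618) = 2.8 months. Medians of 2 and 3 give 2.4; 3 and 6 give 4.2.

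Now add the other cohorts. Let a = A-3 plus A-4 subjects and b = A-5 subjects. Give A-5 a median of 12.4 months and everyone else an assumed median m. The 12.4 is the doublet figure in protocol 1.7.3.3, for treatment-naive and treatment-experienced melanoma together. Then t solves

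[(16 + a + p)·0.5^(t/m) + b·0.5^(t/12.4)] / (16 + a + p + b) = 0.5.

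| Row composition | m = 2 | m = 3 | m = 4 |
|---|---|---|---|
| b = 0 | 2.0 | 3.0 | 4.0 |
| b = 10, a = 50, p = 9 (full planned sequencing) | 2.3 | 3.4 | 4.4 |
| b = 10, a = 0, p = 3 (extreme) | 3.2 | 4.5 | 5.6 |

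The values of m have no source in the documents. At full planned sequencing enrollment the shift is only 0.3 to 0.45 months.

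**4. How precise would a split be?**

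Assume 8 subjects, true exponential median 3 months, no censoring, 4000 simulated data sets, and the Brookmeyer-Crowley interval named in the SAP. Typical 95% limits are about 0.4 to 6.9 months (log-log form) or 1.0 to 6.9 (linear form). With assumed uniform censoring over 1 to 12 months, the upper limit is not estimable in about 32% (linear) to 41% (log-log) of data sets.

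**The case against.** The strongest case against is that this is an ambiguity. SAP section 7 never says dose level in its visible text, the one grouping it does state is tumor type, and the SAP describes itself as detailing analyses outlined in the protocol. A programmer could fill the gap from the synopsis. That is possible, but nothing in the visible SAP directs it, and other silent sections depend on 5.2.

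It is also fair that the objectives name the populations in one sentence without saying separately, and that cohort can mean a dose cohort in Part 1. In Part 2, however, cohorts A-1 and A-2 are defined by tumor type.

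Much of the rest stands. SAP 5.2 gives the stop of enrollment as its context. The analyses are descriptive. Protocol 9.4.2 makes PFS and DOR estimation conditional. ORR, the Part 2 primary endpoint, is already split, and Listing 2.6.2 shows PFS by subject. With about 8 per cohort a split median is very imprecise. Small numbers are a reason to list subjects, though, not to merge unlike diseases.

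A reader might infer that the sponsor dropped the by-cohort analysis without saying so. The documents do not support that: SAP 10.1 is partly redacted or absent, so a disclosure there cannot be excluded.

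**Conclusion.** The concern holds for PFS as a gap in the SAP. Its only visible grouping rule gives a median pooled across tumor types and lines of therapy, which does not address the NSCLC and MSS CRC objectives in SAP 2.2.2 and departs from the synopsis. For DOR it is only possible, because of the shared table.

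Two stronger readings should be resisted. One is that no PFS estimate for these tumor types is planned anywhere; the protocol plans it by cohort. The other is that the shares and pooled medians above measure the distortion. Actual enrollment is not given, the cohort medians are assumed, and the 42% to 9% range is not a bound, so the size of the effect cannot be stated.

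This should be corrected, but it affects descriptive secondary endpoints in a study that stopped early.

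**What to change.** In SAP 7.2.3 and 7.2.5, and in Tables 2.1.1 and 2.2.1, state that DOR and PFS are presented by cohort-specific tumor type as for ORR, subject to the protocol's condition that there are sufficient observations. Keep dose-level pooling for the safety tables.

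The change needs SAP wording and extra table columns, and no new data. The downside is that with small cohorts the intervals will be wide and some medians or confidence limits will not be estimable.
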